6.13 PSYCHOMETRIC ANALYSIS OF THE PGI-S ITEMS

The following analyses will be conducted on the PAP.

6.13.1 *Validity of the PGI-S Items*

A number of specific forms of validity exist, but one of the most important to the present study is construct validity, which describes the relationships among multiple indicators of a construct and the degree to which they follow predictable patterns. Correlations will be computed between PGI-S scores and in Borg Dyspnea scores, oxygen saturation, and HR. The goal is to

demonstrate stronger relationships among measures addressing similar constructs as compared with measures addressing more disparate constructs. Correlations will be computed using data collected at the same or nominally similar time points, specifically, at Baseline (pre-ISWT average of -15 minutes and 0 minutes) and post-ISWT (1, 2, 3, 4, and 5 minutes).

Inferences regarding validity are based on the patterns of correlations among the measures. Cohen (1992) provides the following guideline for interpreting correlation coefficients: absolute values of correlations of 0.50 or greater are considered strong, correlations that fall between 0.30 and 0.49 are moderate, and those between 0.10 and 0.29 are small.

Higher scores on the PGI-S items, Modified Borg scale, and HR indicate worse outcomes, while higher oxygen saturation is a better outcome. Therefore, positive correlations are expected between the PGI-S items and the Modified Borg scale and HR, and negative correlations are expected between the PGI-S items and oxygen saturation. Furthermore, the following are hypothesized:

- The PGI-S Overall item will be at least moderately correlated ($|r| > 0.30$) with oxygen saturation and with HR
- The PGI-S Shortness of Breath item will be at least moderately correlated with the Modified Borg score, oxygen saturation, and HR
- The PGI-S Physical Fatigue item will be at least moderately correlated with oxygen saturation and HR

To further support the construct validity of the PGI-S, correlations will also be computed between PGI-S change scores and change in Borg Dyspnea scores, oxygen saturation, and HR. These correlations will allow us to evaluate potential improvements (or declines) in the severity of symptoms commonly associated with PAH (as assessed by the PGI-S) and any corresponding improvements (or declines) in subjects' clinical measures. Correlations will be computed between changes from Baseline (pre-ISWT average of -15 minutes and 0 minutes) and post-ISWT (1, 2, 3, 4, and 5 minutes). Similar to the cross-sectional construct validity hypotheses, it is expected that:

- Change in the PGI-S Overall item will be at least moderately ($|r| > 0.30$) negatively correlated with change in oxygen saturation and at least moderately positively correlated with change in HR

- Change in the PGI-S Shortness of Breath item will be at least moderately positively correlated with change in the Modified Borg score and with change in HR, and at least moderately negatively correlated with change in oxygen saturation
- Change in the PGI-S Physical Fatigue item will be at least moderately negatively correlated with change in oxygen saturation and at least moderately positively correlated with change in HR

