The ISWT is the activity that will be used to induce symptoms of PAH during Screening and on Day 1 of the study. All activities will be conducted in a designated area which meets the requirements described in Appendix 15.2.

Subjects receiving supplemental oxygen during the Screening assessment must continue to receive the same flow rate at all subsequent ISWTs. The supplemental oxygen flow rate must be recorded for each activity, as applicable. Supplemental oxygen therapy must not be introduced for subjects after the Screening assessment, unless there is an urgent medical need in the clinical judgement of the Investigator.

The total number of shuttles completed by a subject during the Screening ISWT will be the maximum targeted for that subject during the remaining ISWTs in the study.

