Summary statistics will be computed to characterize the difference between peak and trough conditions in Cohort A, correlations between conditions, variability measures, and sequence/period effects (as appropriate). Summary statistics will include the mean, N, standard deviation, median, mode, minimum, maximum, the 25th and 75th percentile values, and 95% confidence intervals for the mean and difference values.

6.11.4 *To Assess the Ability of the PGI-S Response Scale to Detect Resolution in Activity-induced Symptoms*

The analysis of PGI-S item-level data will assess the time to resolution of symptoms (return to baseline values) measured *after* completion of the ISWT (ie, change score ≤ 0) for PGI-S Overall PAH Symptoms, PGI-S Shortness of Breath, and PGI-S Physical Fatigue on Day 1. Summary statistics will include frequencies and percentages by protocol-specified evaluations, ie, 0 to 5 minutes, >5 to 10 minutes, etc, by cohort.

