6.12 SUPPORTIVE ANALYSES

6.12.1 *Borg Dyspnea Score*

Summary statistics will be computed to characterize average change and variability overall and by cohort and sequence/period (as appropriate). The pre-ISWT (average of -15 and 0 minutes), post-ISWT at each time point, and pre-post difference for Borg Dyspnea score will be provided. Summary statistics will include the mean, N, standard deviation, median, mode, minimum, maximum, the 25th and 75th percentile values, and 95% confidence intervals for the mean and difference values.

6.12.2 *Pulse Oximetry and Heart Rate*

Summary statistics will be computed to characterize average change and variability overall and by cohort and sequence/period (as appropriate). The pre-ISWT (average of -15 and 0 minutes), post-ISWT at each time point, and pre-post difference for oxygenation and HR will be provided. Summary statistics will include the mean, N, standard deviation, median, mode, minimum, maximum, the 25th and 75th percentile values, and 95% confidence intervals for the mean and difference values.

6.12.3 *ISWT*

Tabulations will be provided by cohort and sequence/period (as appropriate) for the total number of shuttles completed, total distance walked (meters), use of oxygen during ISWT (Yes, No), reason for ISWT ending (Shortness of breath, Physical fatigue, Chest pain, Other), and time since most recent dose of PAH medication (Start time of ISWT - Time of most recent dose of PAH medication).

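### The PGI-S/SpO2 correlations do not separate walks on supplemental oxygen from room-air walks, so the |r| > 0.30 hypotheses can be distorted in either direction

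*SAP*

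**What the plan says.** Protocol 3.3.4.1 lets subjects who use oxygen at Screening take part and holds their flow constant at later walks. On new oxygen it says: "Supplemental oxygen therapy must not be introduced for subjects after the Screening assessment, unless there is an urgent medical need". On data capture it says: "The supplemental oxygen flow rate must be recorded for each activity, as applicable".

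SAP 6.13.1 sets out the validity analysis: "Correlations will be computed between PGI-S scores and in Borg Dyspnea scores, oxygen saturation, and HR". For the overall item the hypothesis is that it will be "at least moderately correlated ($|r| > 0.30$) with oxygen saturation and with HR". The shortness-of-breath and fatigue items carry the same hypothesis for SpO2. The section then adds that "correlations will also be computed between PGI-S change scores and change in Borg Dyspnea scores, oxygen saturation, and HR", again with at least moderate correlations expected. On interpretation it says: "Inferences regarding validity are based on the patterns of correlations among the measures".

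Oxygen appears once in the planned analyses, in SAP 6.12.3, as a tabulation of "use of oxygen during ISWT (Yes, No"). The subgroup text in SAP 6.13.3 names demographic, cohort and disease factors, not oxygen. SAP 6.11.4 will "assess the time to resolution of symptoms (return to baseline values"), meaning a change score of zero or less, summarised by time band and cohort.

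**The concern.** SpO2 is one of the measures against which the PGI-S items are to be validated, and supplemental oxygen acts on it directly. Subjects who walk on oxygen are also likely, though the documents do not say so, to have worse symptoms. When two groups differ on both variables, the pooled correlation mixes the within-group relationship with the difference between groups. A coefficient that misses or meets 0.30 may then say more about who was on oxygen than about the PGI-S item.

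The relationship of PGI-S with oxygen saturation is a named secondary objective, and the SpO2 hypothesis applies to every item. The data needed to separate the two groups are already collected. The per-protocol set gives no alternative view of these correlations: SAP 6.13 runs on the Psychometric Analysis Population, and the table list has the construct-validity table for that population only.

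The recovery table raises a smaller, related point. If oxygen is started under the urgent-need exception, the baseline precedes it and later PGI-S readings follow it. The 6.12.3 row covers oxygen during the walk, so oxygen begun in recovery would not show there.

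**Working it through.** The plan derives no figure for this analysis. The 0.30 limit is a published convention for a moderate correlation, so the check is how far pooling can move r relative to it.

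**Inputs from the documents:** limit |r| > 0.30, negative sign expected for SpO2; 36 evaluable subjects.

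**Assumed inputs (not in the documents):** within-group r (ρ) of -0.40; SpO2 SD of 4 points; share on oxygen (p) of 20% or 30%; oxygen users 0.5 or 1 SD more symptomatic (d_P); SpO2 lift of -2 to +6 points in oxygen users at a given symptom level.

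**Formula** for two groups with common within-group correlation ρ:

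pooled r = [ρ + p(1-p)·d_S·d_P] / √{[1 + p(1-p)·d_S²]·[1 + p(1-p)·d_P²]}

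Here d_S = ρ·d_P + lift/4. The first term lets sicker oxygen users desaturate more, as ρ implies.

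**Worked cases**, p = 0.30, so p(1-p) = 0.21:

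- Lift +4, d_P = 0.5: d_S = -0.20 + 1.00 = 0.80; r = (-0.40 + 0.084)/√(1.1344 × 1.0525) = -0.316/1.0927 = -0.289.
- Lift +4, d_P = 1: d_S = 0.60; r = (-0.40 + 0.126)/√(1.0756 × 1.21) = -0.274/1.1408 = -0.240.
- Lift -2, d_P = 1: d_S = -0.90; r = (-0.40 - 0.189)/√(1.1701 × 1.21) = -0.589/1.1899 = -0.495.

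**Pooled r when the within-group r is -0.40:**

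| Lift (points) | 20% on oxygen, d_P 0.5 | 20%, d_P 1 | 30%, d_P 0.5 | 30%, d_P 1 |
|---|---|---|---|---|
| -2 | -0.43 | -0.48 | -0.44 | -0.50 |
| 0 | -0.41 | -0.43 | -0.41 | -0.43 |
| +2 | -0.37 | -0.36 | -0.36 | -0.34 |
| +4 | -0.31 | -0.27 | -0.29 | -0.24 |
| +6 | -0.26 | -0.19 | -0.22 | -0.14 |

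A simulation with a five-category item agrees with the formula. For ρ = -0.45, 20% on oxygen, and both SpO2 and PGI-S 1 SD higher in oxygen users, the formula gives -0.25. The simulated item gives -0.24 pooled and -0.43 among room-air subjects.

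**Set against sampling error**, one walk per subject, n = 36, Fisher z: P(|r| ≤ 0.30) = Φ{[atanh(0.30) - atanh(|r|)]·√33}.

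- True r -0.40: Φ(-0.66) = 26%.
- Pooled r -0.289: Φ(0.07) = 53%.
- Pooled r -0.240: Φ(0.37) = 64%.

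**Change scores.** If oxygen is already running before the walk, a constant lift is in both the baseline and the later reading and cancels. A smaller fall in SpO2 on oxygen does not cancel, nor does oxygen started after baseline. The change correlations use minutes 1 to 5 after the walk, when such oxygen could be running. No size was computed for this part.

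**The case against.** The strongest objection is that the direction and size are assumed. A reader might infer that pooling must pull r toward zero or reverse it. The documents do not support that. Oxygen users may remain the more desaturated group, and r then becomes stronger. No computed case changes sign. At a 2-point lift no cell misses 0.30, and at 10% use only the most extreme cell (6 points, 1 SD) does, at -0.27. This stands, and it is why the point is stated as distortion in either direction.

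A reader might also infer that one coefficient below 0.30 fails an item. SAP 6.13.1 rests validity on the pattern of correlations, SAP 6.10 says hypothesis testing does not apply, and sampling error alone gives a 26% chance of a miss at a true r of -0.40. That limits the consequence, but SpO2 is an explicit part of the pattern for every item.

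On recovery, a reader might infer that oxygen-assisted recovery is being passed off as natural recovery. Neither document describes recovery as natural or unaided. SAP 6.11.4 asks whether the scale detects return to the subject's own pre-walk score, and resolution helped by oxygen is still resolution. For stable users the fixed flow and own-baseline comparison give protection. Only the urgent-need exception is left, and its frequency is unknown.

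Nor do the documents show that the per-protocol set would necessarily keep such walks. Its definition also asks whether subjects were appropriately included, with sponsor review at database lock.

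Finally, judging the SpO2 hypotheses on room-air walks alone would narrow the population. At 30% use, n falls from 36 to about 25. The standard error on the Fisher scale rises by √(33/22) - 1 = 22%, and the chance of a miss at r = -0.40 goes from 26% to 30%. That is a reason to show both analyses.

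**Conclusion.** The point holds in a limited form. Oxygen use is permitted, recorded for each walk and bears directly on SpO2, yet the planned PGI-S/SpO2 correlations take no account of it. With ρ = -0.40 and 20% to 30% of subjects on oxygen, pooled r runs from about -0.37 to -0.14 for a 2- to 6-point lift. It runs from about -0.41 to -0.50 for no net lift or a 2-point lower SpO2. These ranges depend on an oxygen share, a symptom difference and an SpO2 difference that the documents do not give; the omission itself rests on the text alone.

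Level correlations are the most affected, and change correlations less so. The recovery table merits a sensitivity analysis, no more. The documents do not establish that valid items will miss the limit, or that the recovery profile is wrong.

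**What to change.** In SAP 6.13.1, keep the all-walks correlation. Pre-specify beside it, for both level and change, (a) the PGI-S/SpO2 correlations by oxygen use, room air versus oxygen, and (b) a partial correlation adjusting for oxygen use. State that the |r| > 0.30 hypotheses for SpO2 will be read with both. If the within-group correlation is common to the two groups, the partial correlation recovers it whichever way pooling distorts r; in the assumed cases above that is -0.40.

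In SAP 6.11.4, as a sensitivity analysis only, repeat the time-to-resolution table without walks in which oxygen was newly introduced or the flow differed from Screening. Oxygen first started in recovery can be identified only if the per-walk oxygen record extends to recovery, so that should be confirmed.

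The cost is SAP wording and one extra table split, using the oxygen flow already recorded. The downside is a small oxygen stratum. With 30% of 36, about 11 subjects, an observed r of -0.40 has a 95% Fisher interval of tanh(-0.424 ± 1.96/√8), or -0.81 to 0.26, so that stratum is descriptive. Because SAP 7.4 allows data to be evaluated at any time, the analyses should be written down before SpO2 correlations are seen; otherwise oxygen use becomes an after-the-fact explanation.

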5.1 OBSERVATIONAL ENDPOINTS

5.1.1 *Patient Global Impression of Severity*

The primary objective is to characterize the psychometric properties and performance of the 3 PGI-S items, measuring overall PAH symptoms, shortness of breath, and physical fatigue during pre-ISWT, at the end of activity, and through recovery.

The focus of each item, separately, will be the subject's evaluation of:

1. Overall PAH Symptoms: [REDACTED]
2. Shortness of Breath: [REDACTED]
3. Physical Fatigue: [REDACTED]

Subjects will be asked to rate each item based on their level of symptom severity "at this moment" using a 5-point ordinal response scale (1=Not present, 2=Mild, 3=Moderate, 4=Severe, 5=Very severe). The timing of the assessments for Overall PAH Symptoms, Shortness of Breath, and Physical Fatigue scales will be at Screening/Baseline (-15 minutes and at 0 minutes

prior to activity-inducement of PAH symptoms), at completion of the ISWT, and every 1 minute for 5 minutes then every 5 minutes following completion of the ISWT during recovery. The average recovery time of symptoms is unknown but, based on clinician advice, it is expected that recovery should be within 15 to 20 minutes. Assessments for PGI-S will occur for 30 minutes following completion of the ISWT to ensure that the full recovery profile is captured across all subjects observed.

For each PGI-S item, a change from Baseline score will be calculated for the PGI-S items measured from the start of the activity-inducement of PAH symptoms.

5.1.2 *Modified Borg Dyspnea Score*

The Modified Borg Dyspnea score (see Section 9) will be completed by subjects as follows: Subjects will be asked to rate dyspnea “at this moment” on an 11-point numeric rating scale (0=Nothing at all, 10=Maximal) at Screening/Baseline (-15 minutes and at 0 minutes prior to activity-inducement of PAH symptoms) and at completion of the ISWT.

5.1.3 *Oxygen Saturation and Heart Rate*

Oxygen saturation and HR will be measured continuously throughout the observation period with measurements extracted and recorded into eCRFs at Screening/Baseline (-15 minutes and at 0 minutes prior to activity-inducement of PAH symptoms), each minute during the ISWT, at completion of the ISWT, and every 1 minute for 5 minutes then every 5 minutes following completion of ISWT during recovery. Key measurements used for analysis will be those that correspond to the measurement of the PGI-S and Borg Dyspnea scores.

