6.13.2 Response Frequency Distributions

To examine floor and ceiling effects for each PGI-S item, the percentage of subjects reporting the worst and best possible item scores will be examined in the context of the item-level response frequency distributions. A floor effect occurs if the worst response category (5=Very severe) is the mode of the empirical distribution and at least 2 times the expected percentage of subjects (given a uniform distribution) who select this response category. Similarly, a ceiling effect occurs if the best response category (Not present) is the mode of the empirical distribution and at least 2 times the expected percentage of subjects (given a uniform distribution) who select this response category. In the case of the PGI-S items, which have 5 response categories, the expected percentage of subjects given a uniform distribution is 20%; a floor or ceiling effect would require that more than 40% of the subjects select the worst or best response category, respectively.

PGI-S response frequency distributions will be tabulated and examined at Baseline (pre-ISWT average of -15 minutes and 0 minutes), when symptoms are expected at their minimal level, and post-ISWT (0 minutes), when symptoms are expected at their maximum level. Distributions will be provided for all subjects and visits/periods combined, as well as individually within Cohorts and visits/periods (Screening, Day 1 Period 1, and Day 1 Period 2).

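### SAP 6.13.1 judges its |r| > 0.30 validity hypotheses on point estimates with no deciding time and no interval, and leaves out ISWT completion, the expected symptom peak and the only post-walk Borg reading

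*SAP*

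**What the plan says.** SAP 6.13.1 computes correlations of the PGI-S items with Borg, oxygen saturation and HR at matching or nominally similar "time points, specifically, at Baseline (pre-ISWT average of -15 minutes and 0 minutes) and post-ISWT (1, 2, 3, 4, and 5 minutes". It then states seven level hypotheses: two for the Overall item, three for Shortness of Breath and two for Physical Fatigue. The first is that the Overall item "will be at least moderately correlated ($|r| > 0.30$) with oxygen saturation and with HR". Direction is fixed beforehand: "positive correlations are expected between the PGI-S items and the Modified Borg scale and HR", and negative ones with oxygen saturation.

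The same section repeats the bar for seven change-score hypotheses: "Correlations will be computed between changes from Baseline (pre-ISWT average of -15 minutes and 0 minutes) and post-ISWT (1, 2, 3, 4, and 5 minutes". On how the results are read, it says "Inferences regarding validity are based on the patterns of correlations among the measures".

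Other places that bear on this:
- SAP 6.13.2 describes Baseline as the time "when symptoms are expected at their minimal level", and contrasts it with "post-ISWT (0 minutes), when symptoms are expected at their maximum level".
- SAP 5.1.1 rates each item on a "5-point ordinal response scale (1=Not present, 2=Mild, 3=Moderate, 4=Severe, 5=Very severe").
- SAP 5.1.2 and Protocol 3.3.4.3 collect Borg after the walk only once, at completion (within 1 minute in the Protocol).
- SAP 6.11 and 6.12 give 95% intervals for means and differences, not for correlations. Protocol 10.3 makes intervals optional and informal.
- SAP 6.10 marks hypothesis testing as not applicable.

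**The concern.** Psychometric performance is the primary objective, and SAP 6.13.1 counts construct validity among the most important forms of validity for this study. Each level hypothesis on HR or SpO2 can be read from six correlations and each change hypothesis from five. Nothing says beforehand which one counts.

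The list of times also fits the purpose poorly. It includes rest, where the SAP expects the least symptom, and omits completion, where it expects the most. For Borg the consequence is direct: there is no 1 to 5 minute Borg score, so following the list pairs a completion Borg score with PGI-S ratings given during recovery, although a completion PGI-S rating exists. Shortness of Breath with Borg is the one hypothesis in which both measures address the same symptom.

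Finally, a numeric bar is read on bare point estimates from a small sample. A reader of the report could not tell how firmly a value just above or below 0.30 was established.

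**Working it through.** **Inputs.** From the documents: the bar of 0.30; rest plus five post-walk minutes (SAP 6.13.1); 36 evaluable subjects (SAP 4); five ordered categories (SAP 5.1.1). Assumed, because the documents give no figure: one record per subject, correlation between successive minutes of 0.7 to 0.9, and the resting distribution of ratings. The plan's only precision figure concerns mean PGI-S change, so there is no stated figure for correlations to reproduce.

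**1. Precision of r = 0.30 at n = 36 (Fisher z).**
atanh(0.30) = 0.3095; SE = 1/√33 = 0.1741; 0.3095 ± 1.96 × 0.1741 = -0.032 to 0.651. Back-transformed: **-0.03 to 0.57**. For one cohort of 20 the same method gives -0.16 to 0.66.

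**2. An unrelated item at one named time.**
t = 0.30 × √34 / √(1 - 0.09) = 1.834 on 34 df. P(|r| > 0.30) = 7.5%; in the expected direction, **3.8%**.

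**3. The same item if any one of five minutes may count (HR or SpO2).**
If the minutes were independent: 1 - (1 - 0.0377)^5 = 17.5% in the expected direction. Simulation with first-order autocorrelation in both measures:

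| Autocorrelation | Expected direction | Either direction |
|---|---|---|
| 0.9 | 11% | 22% |
| 0.8 | 13% | 26% |
| 0.7 | 15% | 29% |

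The SAP fixes the sign, so the middle column applies. None of this applies to Borg, which has one post-walk reading.

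**4. The opposite reading: all five minutes must pass.**
In the same simulation an unrelated item then passes in about 0.3% of runs or fewer. An item with a true r of 0.40 passes in about 37% to 52% of runs, against 93% to 99% if any one minute is enough. The result depends on a rule the SAP does not state.

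**5. Attenuation at rest.**
For a latent correlation ρ and an item cut at normal points c_j, expected r = ρ × Σφ(c_j) / SD(item score). Example with 80/17/2.5/0.4/0.1% across the categories: Σφ = 0.366, SD = 0.516, ratio 0.709, so 0.40 becomes 0.28.

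| 'Not present' at rest (assumed) | Latent 0.40 becomes about |
|---|---|
| 40% | 0.36 |
| 60% | 0.33 |
| 80% | 0.28 |
| 90% | 0.23 |

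This uses a single rating. The SAP averages two, which allows half-steps, so the figures are approximate.

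**6. Effect of adding a rule that the CI must exclude 0.**
At n = 36 the lower limit clears 0 at r = tanh(1.96 × 0.1741) = 0.33. For a true r of 0.40, the chance of missing 0.30 is Φ((0.3095 - 0.4236) × √33) = 26%. The chance of missing 0.33 is Φ((0.3412 - 0.4236) × √33) = 32%.

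**The case against.** The strongest reply is that SAP 6.13.1 contains no pass/fail rule. It judges by pattern, SAP 6.10 excludes hypothesis testing, and weak correlation at rest with stronger correlation after the walk is itself a readable pattern. That stands as far as it goes. A reader might infer that the plan both fails valid items and passes unrelated ones. The documents do not support that: the first needs the resting correlation to count on its own, the second needs any single minute to be enough, and no one rule gives both. What the reply does not answer is that numeric hypotheses are stated in advance while the time that decides them is left open.

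A reader might also infer a false-pass rate of 21% to 29%. That ignores the sign that the SAP fixes.

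A third tempting inference is that most resting ratings will be 'Not present'. SAP 6.13.2 says only that symptoms are expected to be lowest at rest. With 40% in that category the loss is small, and 6.13.2 will tabulate the resting distribution against its own 40% criterion, so crowding would be visible.

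It can also be said that the completion reading, taken within 1 minute, is close to the 1-minute reading. But SAP 6.13.2 and 6.13.5 treat 0 minutes post-walk as its own time point, and a completion PGI-S rating is there to be used.

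**Conclusion.** The point holds as a gap in specification with a practical consequence. The |r| > 0.30 hypotheses, both level and change, have no deciding time, no named visit or period and no interval. The list of times omits completion, where symptoms should peak and where Borg is measured.

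The size that can be stated without knowing the reading rule is the imprecision: r = 0.30 at n = 36 is compatible with anything from -0.03 to 0.57. The open choice of minute would raise the chance of a correct-sign pass by an unrelated HR or SpO2 pairing from 3.8% to about 11% to 15%, but only if any one minute were accepted. Loss at rest ranges from slight to substantial, depending on a distribution that the documents do not give.

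All n = 36 figures assume one record per subject. Pooling Screening and both Day 1 periods would give up to 3 × 36 = 108 records, but they are not independent, and SAP 6.13.1 does not say whether they are pooled.

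**What to change.** Amend SAP 6.13.1, for level and change hypotheses alike:
- Judge the Borg hypotheses on the PGI-S and Borg readings at ISWT completion.
- For HR and SpO2, name in advance one post-walk figure, for example the completion reading or each subject's mean over minutes 1 to 5, with PGI-S taken over the same time. SAP 5.1.3 lists a completion reading for HR and SpO2, but the recording schedule in Protocol 3.3.2.3 does not name one, so confirm that the eCRF holds it before choosing completion.
- Name the visit or period, with one record per subject.
- Keep resting and other-minute correlations as description.
- Print a 95% CI beside every correlation, and judge each hypothesis on the expected sign and the 0.30 bar with the CI in view.

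Do not add a requirement that the CI exclude 0. At n = 36 that only moves the bar from 0.30 to about 0.33 and raises misses at a true r of 0.40 from 26% to 32%.

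The cost is SAP wording, slightly more output, and less freedom to choose which correlation to cite.

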^d See Appendix 15.3. The subject should be asked to rate his/her maximal breathlessness at pre-ISWT (-15 and 0 minutes prior to activity inducement of PAH symptoms) and immediately at the end of the ISWT (within 1 minute of completing the activity). Assessments will be recorded in the subject's source documents and eCRF.

^e Assessed at pre-ISWT (-15 and 0 minutes prior to activity inducement of PAH symptoms), at the end of the ISWT (within 1 minute of completing the activity), every minute for the first 5 minutes of the recovery, followed by every 5 minutes for the remainder of the 30-minute recovery. Assessments will be recorded in the subject's source documents and eCRF. Assessments will be performed in the following order: 1) PGI-S global PAH question; 2) PGI-S shortness of breath question; 3) PGI-S physical fatigue question. PGI-S assessments are to be conducted prior to the Borg dyspnea score assessments.

^f Pulse oximetry to be performed continuously. Pulse oximetry will include the collection of SpO₂ and HR. Pulse oximetry will start at the beginning of pre-ISWT (15 minutes prior to the ISWT) and will be continuous through the end of recovery of each individual period. The SpO₂ and HR measures obtained at -15 and at 0 minutes (prior to activity), every minute during the ISWT, every minute for the first 5 minutes of the recovery, followed by every 5 minutes for the remainder of the 30-minute recovery will be recorded in the subject's source documents and eCRF.

^g All AEs will be documented from time of informed consent until the subject discontinues or subject completes the study.

^h Subjects will be provided at least a 1-hour period for rest between ISWTs (until subject feels they are rested enough to perform again at their baseline level) prior to Period 2 assessments. The start and end times for this period should be documented in subject's source documents and eCRF.

ⁱ Includes PAH history and WHO Functional Class. Any significant changes to the subject's medical condition must be documented throughout the course of the study.

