6.9 ANALYSIS OF ENDPOINTS

The primary objective is to assess the psychometric properties and performance of the PGI-S items.

The focus of the analyses will be to describe the responsiveness to change of the PGI-S items to the subjects' self-reported symptoms of PAH at the end of the activity and during recovery from the activity. The Sponsor will tabulate the relevant symptom scores and compute change from Baseline (pre-activity) scores for each item. Data may be displayed graphically and will be summarized overall and by cohort and sequence/period (as appropriate).

Additionally, for Cohort A, the sensitivity to a known inhaled treprostinil drug effect will be assessed. Tabulations will be made across sequences/periods for the PGI-S measurements with inhaled treprostinil to PGI-S measurements without inhaled treprostinil. Test-retest assessments for PGI-S measurements will be conducted for Cohort B.

Correlations between the 3 PGI-S questions and with Borg dyspnea scores, oxygen saturation, and HR will be assessed. Data for HR recovery at 1 minute after the ISWT will be examined in an exploratory fashion overall and as related to PGI-S measurements.

The onset and recovery profile for activity-induced symptoms will also be characterized.

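### The construct-validity correlations in SAP 6.13.1 leave out the end-of-walk time point, the only post-exercise time at which Borg is scheduled

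*SAP*

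**What the plan says.** SAP 6.13.1 plans correlations of the PGI-S items with Borg, oxygen saturation and heart rate, first as levels and then as changes. For levels the general rule is that "Correlations will be computed using data collected at the same or nominally similar time points", and the times are then spelled out: "at Baseline (pre-ISWT average of -15 minutes and 0 minutes) and post-ISWT (1, 2, 3, 4, and 5 minutes"). For changes, correlations are computed "between changes from Baseline (pre-ISWT average of -15 minutes and 0 minutes) and post-ISWT (1, 2, 3, 4, and 5 minutes").

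The stated aim is to "demonstrate stronger relationships among measures addressing similar constructs as compared with measures addressing more disparate constructs". One of the hypotheses is: "Change in the PGI-S Shortness of Breath item will be at least moderately positively correlated with change in the Modified Borg score".

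The Borg schedule is narrower than these lists. SAP 5.1.2 places the score at minus "15 minutes and at 0 minutes prior to activity-inducement of PAH symptoms) and at completion of the ISWT". Protocol Table 3-1, footnote d, gives the same pre-walk times "and immediately at the end of the ISWT (within 1 minute of completing the activity"), and the Recovery columns of that table carry no Borg mark. Protocol 3.3.4.3 agrees.

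SAP 6.9 makes a broader commitment with no times attached: "Correlations between the 3 PGI-S questions and with Borg dyspnea scores, oxygen saturation, and HR will be assessed".

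**The concern.** The PGI-S items, oxygen saturation and heart rate are all recorded each minute for the first five minutes of recovery. Borg is not. A list that runs from Baseline straight to 1 minute therefore skips the one post-exercise moment at which a PGI-S answer and a Borg score are taken together.

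This affects the pair that matters most for the section's stated aim. PGI-S Shortness of Breath with Borg is the only hypothesised pair in which both measures are the patient's own rating of breathlessness, so it is the natural anchor for showing that similar constructs correlate more strongly than dissimilar ones. The relationship of PGI-S with Borg is also the first item of the first secondary objective.

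Followed literally, the plan gives that pair matched data only at rest, where SAP 6.13.2 expects symptoms to be minimal, and none for change. The analyst would have to drop a pre-stated hypothesis or choose a pairing that the SAP does not specify. SAP 7.4 allows the data to be evaluated at any time, so that choice could be made after results have been seen.

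**Working it through.** The plan gives no figure of its own to reproduce here. The check compares scheduled times with listed times.

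**Inputs**

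| Item | Times | Source |
|---|---|---|
| Borg | -15 and 0 minutes pre-ISWT; completion | SAP 5.1.2; protocol 3.3.4.3; Table 3-1, footnotes d and k |
| PGI-S | -15 and 0 minutes pre-ISWT; completion; 1, 2, 3, 4, 5, 10, 15, 20, 25, 30 minutes | Protocol 3.3.4.2; Table 3-1, footnote e |
| SpO2 and HR | Pre-ISWT; during the walk; completion; same recovery times as PGI-S | SAP 5.1.3 |
| Level correlations | Baseline; 1, 2, 3, 4, 5 minutes (6 times) | SAP 6.13.1, first list |
| Change correlations | 1, 2, 3, 4, 5 minutes (5 times) | SAP 6.13.1, second list |

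**Are completion and 1 minute the same time?** No. Footnote e lists the end-of-walk assessment and then the minute-by-minute recovery assessments. SAP 6.13.2 and 6.13.5 also use 0 minutes post-ISWT as a time of its own.

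**Is Borg collected in recovery under some other heading?** No. Protocol 7.1.3 mentions Borg in its Screening recovery list, but only in a remark on the order of PGI-S and Borg; Borg is not an item in that list. SAP 6.12.1 refers to each post-ISWT time point when describing the Borg summary, but schedules no further score.

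**Overlap**

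- Times with both PGI-S and Borg: Baseline and completion.
- Of these, listed for levels: Baseline only.
- Of these, listed for changes: none.

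**Counts, per visit or period.** Pairs: 3 PGI-S items × 3 comparators = 9, of which 3 involve Borg and 6 involve SpO2 or HR.

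| | Total | Borg | Borg matched | SpO2/HR | SpO2/HR matched |
|---|---|---|---|---|---|
| Levels | 9 × 6 = 54 | 3 × 6 = 18 | 3 × 1 = 3 | 6 × 6 = 36 | 36 |
| Changes | 9 × 5 = 45 | 3 × 5 = 15 | 0 | 6 × 5 = 30 | 30 |
| Both | 99 | 33 | 3 | 66 | 66 |

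Unmatched Borg correlations: 33 - 3 = 30.

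**Hypothesised pairs in each list.** Overall 2 + Shortness of Breath 3 + Physical Fatigue 2 = 7, of which 1 involves Borg. That pair is matched at 1 of 6 level times and 0 of 5 change times.

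**If the end-of-walk Borg may be paired with the 1-minute PGI-S.** This adds 3 level and 3 change correlations, leaving 30 - 6 = 24 of 33 unmatched.

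**With completion added and Borg limited to its own times.** Levels 3 × 2 = 6, changes 3 × 1 = 3, so 9 Borg correlations, all matched. The hypothesised pair is then matched at 2 of 2 level times and 1 of 1 change time.

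**The case against.** The strongest reply is that 6.13.1 allows data from near-coincident times. Every SpO2 and HR value already exists at the listed times, so Borg is the only comparator for which that allowance has any work to do, and a score taken within a minute of stopping sits next to the 1-minute time. SAP 6.9 and protocol 10.3.2 also promise PGI-S/Borg correlations without restricting the time. SAP 5.1.3 says the key oximetry values are those that correspond to PGI-S and Borg measurements, which points to completion. On this view the objective still has an analysis and one list is merely incomplete.

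Part of this stands. The end-of-walk correlation is not barred, and the Borg side of any pairing is fixed because there is only one post-walk score. But the allowance is followed at once by a specific list, and it is not repeated in the change-score paragraph. At best it would pair Borg with the 1-minute PGI-S and pass over the completion PGI-S, which footnote e places just before Borg in the same assessment. SAP 6.9 names no time, and 5.1.3 governs which SpO2 and HR values are used, not when Borg is correlated.

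A second objection concerns the counts: a time list shared by three comparators need not mean that each is measured at every time, so many of the 30 unmatched correlations are empty by construction. That is a fair caution. In usable results, the correction takes the Borg correlations from 3 to 9; for the hypothesised pair it adds one level and one change correlation. Only one of the three Borg pairs carries a stated hypothesis about strength.

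Third, the layout of Table 14.2.3.2 cannot be checked. The SAP gives only its title and population and says that mock-ups of unique tables are in a separate document.

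**Conclusion.** The concern holds. As written, SAP 6.13.1 cannot produce a time-matched Shortness of Breath/Borg change correlation at any listed time (0 of 5), and it produces the level correlation only at rest (1 of 6). Over the three PGI-S items, 30 of 33 listed Borg correlations have no Borg score at the stated time, or 24 of 33 if the 1-minute pairing is accepted. The counts assume that the time lists apply to all three comparators, as the text reads, and that Borg is collected only as scheduled.

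The consequence is limited. The study is descriptive, SAP 6.10 plans no hypothesis testing, and the completion scores for both measures are collected. It should still be corrected, because a specific rule fails to deliver a pre-stated validity hypothesis that serves the first secondary objective.

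**What to change.** In both paragraphs of SAP 6.13.1, add 0 minutes post-ISWT (completion). State that Borg correlations are computed at Baseline and 0 minutes post-ISWT for levels and at 0 minutes only for changes, using the PGI-S and Borg scores from the same end-of-walk assessment. Keep 1 to 5 minutes for SpO2 and HR; adding completion for these is optional, using the values already listed in SAP 5.1.3. Make Table 14.2.3.2 follow the same times.

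The cost is one time point in two sentences and in one table. The change from Baseline at completion is already planned for PGI-S in SAP 6.11.1, and the Borg pre-post difference in 6.12.1. No protocol, eCRF or sample-size change is needed.
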